4.1.3.4 Exploratory expansion cohort

Doc. No.: c02304008-15

For the exploratory expansion cohort patients will have received prior enzalutamide, but no prior abiraterone for CRPC, and while on enzalutamide show a rise in PSA according to standard criteria (R13-1642), and section 3.3.2 (inclusion criterion #19), before entry into the trial. Patients may not have received any prior taxane-based chemotherapy before entering this cohort. Approximately 25 patients will be treated with the combination therapy of BI 836845 and enzalutamide at the MTD and/or recommended phase II dose (RP2D). This expansion cohort will allow for further safety, tolerability and PK assessments (including investigation of potential drug-drug interaction), in addition to the evaluation of anti-tumour activity.

The current enzalutamide treatment taken prior to the trial must be continued after patient informed consent and throughout the screening period and up to the day before the dosing with BI 836845. A compliance check of enzalutamide taken prior to the first day of study treatment should be performed to ensure consistent dosing up to the point of entry into the study, see section 4.3.

Safety will be continually assessed and reported accordingly for all repeated cycles of treatment for all patients throughout the phase Ib escalation and at the MTD and/or recommended phase II dose (RP2D).

4.1.4 Drug assignment and administration of doses for each patient

4.1.4.1 Phase Ib tolerability/safety and dose finding phase

Initially, three patients will be treated at the starting dose regimen (75% BI 836845 and 100%) enzalutamide). Dose escalation will be performed according to the rules outlined in Section 4.1.3.3. Dose escalation and entry of patients into the highest dose regimen will begin only after accrual of the required minimum number of patients has been achieved and all patients in the cohort have completed cycle 1 (28 days) of treatment. Patients who are not treated to the end of the first cycle for any reasons other than DLT will be replaced, as per section 3.3.5.

MTD is the highest dose at which no more than one of 6 patients experiences DLT within the initial treatment cycle. Six patients must be treated at the MTD, or recommended phase II dose (RP2D) before commencement of the phase Ib exploratory expansion cohort and phase II.

Trial Protocol Version 12

Doc. No.: c02304008-15 Page 49 of 241 Proprietary confidential information. © 2022 Boehringer Ingelheim International GmbH or one or more of its affiliated companies. All rights reserved.

Prior to inclusion of any new patient, the investigator must confirm the correct dose with the BI Clinical Monitor by means of a fax registration form. If a patient develops a DLT, treatment must be paused and a dose reduction must occur as per the details described in section 4.1.4.4.

BI 836845 vials will be allocated by the IRT system at each weekly visit before study drug administration.

4.1.4.2 BI 836845 (Phase Ib and Phase II - Arm A)

BI 836845 will be given intravenously as a single dose over approximately one hour (60 minutes), with repeated weekly administration on day 1, 8, 15 and 22 of every 28 day cycle of treatment in phase Ib and Arm A in phase II.

BI 836845 will be administered in the exploratory expansion cohort and phase II Arm A, at the MTD and/or recommended phase II dose (RP2D) level determined during phase Ib tolerability and safety (escalation).

Infusion reactions that might occur during infusion with BI 836845, e.g. pyrexia, chills, rigors, dyspnoea, urticaria, bronchospasm, hypotension, hypertension, may be managed by reducing the infusion rate and administering prophylactic antihistamines for subsequent dosing. Severe reactions may require immediate and permanent discontinuation of infusion. A one hour observation period is recommended following each infusion for the first 3 cycles of treatment and at least a 15 minute observation period is recommended following subsequent infusions. See section 4.2.1.1.

Infusion reactions will not be reported on the standard AE page but will be reported on a separate page specifically for infusion reactions in the CRF.

BI 836845 vials will be allocated by the IRT system at every weekly visit.

4.1.4.3 Enzalutamide (Phase Ib and Phase II- Arm A and B)

On the days of infusion, the enzalutamide dose (160mg daily) should be taken in the clinic immediately after the start of the infusion of BI 836845. On all other days patients must take the recommended enzalutamide dose of 160 mg daily, as per the SPC at the same time of day and preferably in the morning.

On the days of PK sampling, enzalutamide must be taken in the clinic, and not at home.

For countries where enzalutamide is supplied, enzalutamide packs will be allocated by the IRT system for every weekly visit and/or the start of every cycle dependent on the part of the trial to which the patients are entered. The supply will cover either a full week (7 days), or a full cycle (28 days), of treatment. Back-up packs will be provided. Replacement packs will also be available for supplies that might be lost by the patient, or where there might be a delay in the first visit of a cycle.

During the COVID-19 pandemic, physical visits to the sites may need to be restricted to ensure patient's safety. Based on a thorough assessment of the benefits and risks, the investigator may still decide to continue the trial treatment and trial medication may be shipped to the patient's home if acceptable according to local law and regulations. The

Doc. No.: c02304008-15 Trial Protocol Version 12 Page 50 of 241

Proprietary confidential information. © 2022 Boehringer Ingelheim International GmbH or one or more of its affiliated companies. All rights reserved.

shipment should occur via a courier approved by the sponsor in order to ensure correct conditions of shipment.

4.1.4.4 Temporary treatment interruption and dose reduction for BI 836845 and enzalutamide during phase Ib and phase II

Drug-related DLTs or those adverse events requiring dose adjustment, will be managed by a pause in treatment followed by a subsequent dose reduction of the relevant medication according to tables 4.1.4.4:1 and 4.1.4.4:2. In phase Ib escalation, BI 836845 and enzalutamide must be paused when a drug-related DLT occurs regardless of the cycle of treatment. In the phase Ib exploratory expansion cohort and phase II, the causal drug(s) should be paused regardless of the cycle of treatment. In both phase Ib and phase II, the patient will be kept on study until both BI 836845 and enzalutamide are permanently stopped and the patient is discontinued.

Table 4.1.4.4: 1 Dose interruption/reduction scheme by AE type and CTCAE Grade (Phase I and II)

AE Type and CTC Grade	Action
 AST or ALT > 5x ULN (for baseline AST/ALT ≤ ULN) or > (baseline value + 4x ULN) (for baseline AST/ALT > ULN) CTCAE Grade 3 or 4 toxicity CTCAE Grade 2 infusion reaction despite adequate pre-medication. CTCAE Grade 2 nausea and/or vomiting persisting for 7 or more days despite antiemetic treatment. Any other study drug related toxicity at any time point during the study considered significant enough to be qualified as AE requiring dose reduction in the opinion of the investigators and confirmed by the safety review with the BI clinical monitor 	In phase Ib escalation both treatments should be paused. In phase Ib expansion and Phase II only causal treatment should be paused. BI 836845 treatment may resume when patient has recovered to grade ≤1 or baseline. Baseline is defined as the CTCAE grade at the start of treatment. Resume treatment at reduced dose according to table 4.1.4.4:2 If patient has not recovered to Grade ≤1 or baseline within 28 days study treatment must be permanently discontinued* Enzalutamide treatment should be withheld for one week or until symptoms improve to ≤ Grade 2, then resumed at the same or a reduced dose if warranted, as per the SPC. Resume treatment at reduced dose according to table 4.1.4.4:2 If patient has not recovered to ≤ Grade 2 or baseline within 28 days, enzalutamide must be permanently discontinued* Dose reductions will only apply to individual patients. Doses of BI 836845 and/or enzalutamide may be reduced independently of one another. Once the treatment dose has

Page 51 of 241

Proprietary confidential information. © 2022 Boehringer Ingelheim International GmbH or one or more of its affiliated companies. All rights reserved.

Table 4.1.4.4: 1 Dose interruption/reduction scheme by AE type and CTCAE Grade (Phase I and II) (continued)

AE Type and CTC Grade	Action
	been reduced, an increase back up to the previous dose will not be permitted.
Seizure (any grade)	Patients who develop seizure must stop enzalutamide; however they will be permitted to continue BI 836845 (in the combination treatment) if deemed appropriate by the investigator and if criteria of removal from trial are not met.
Any unrelated AEs	The study drug(s) may be interrupted for up to 28 days, but no dose reduction should occur unless indicated in the current drug label/SPC of enzalutamide. Otherwise, the decision to continue with the study treatment will be made by the BI Clinical Monitor in agreement with the investigator.

^{*}In the event that the patient is deriving obvious clinical benefit to the judgement of the investigator, e.g. stable disease or an objective response further treatment with the study drug will be decided only after agreement between the investigator and the BI clinical monitor

Dose reduction of BI 836845 and/or enzalutamide:

Either treatment may be resumed at a reduced dose; however only two dose reductions of BI 836845 or enzalutamide will be permitted. If more than two dose reductions of the same drug are required then the patient should be removed from the drug treatment. A patient will be kept on study until both BI 836845 and enzalutamide are stopped. Dose reduction below 500 mg for BI 836845 or 80 mg for enzalutamide will not be permitted. See table 4.1.4.4:2 for details of dose reduction.

Table 4.1.4.4: 2 Allowed dose reductions BI 836845 and enzalutamide

Dose Level	BI 836845 mg weekly total dose	BI 836845 mg weekly total dose	Enzalutamide mg daily total dose
Starting Dose (0)	1000	750	160
1st Reduced Dose (-1)	750	500	120
2 nd Reduced Dose (-2)	500	OFF DRUG	80

Page 52 of 241

Proprietary confidential information. © 2022 Boehringer Ingelheim International GmbH or one or more of its affiliated companies. All rights reserved.

4.1.4.5 Additional cycles of treatment

Patients demonstrating clinical benefit from treatment with the combination of BI 836845 and enzalutamide in phase Ib, and who have recovered from any clinically relevant drug-related AE, are eligible for further treatment cycles as per the Flowchart, until they experience disease progression, or undue toxicities. Safety will be continually assessed in repeated cycles of treatment and reported accordingly.

Patients demonstrating clinical benefit from treatment with the combination of BI 836845 and enzalutamide or enzalutamide alone in phase II, and who have recovered from any clinically relevant drug-related AE, are eligible for further treatment cycles as per the Flowchart, until they experience disease progression, or undue toxicities. Safety will be continually assessed in repeated cycles of treatment and reported accordingly.

4.1.4.6 Preparation of BI 836845

Refer to the ISF for details of the preparation and handling regimen of BI 836845; including information on equipment, infusion procedure and process.

BI 836845 must be diluted in physiological sodium chloride solution (0.9%) in infusion bags. Infusion bags containing BI 836845 diluted solutions should be refrigerated at 2-8°C; at this temperature they must be administered within 24 hours. Infusion bags stored at room temperature must be administered within 6 hours.

4.1.5 Blinding and procedures for unblinding

4.1.5.1 Blinding

This is an open-label study. Blinding is not applicable. However, to reduce bias, the BI study team will be blinded for the aggregated phase II data at the treatment level until the trial database lock (see Section 3.2 and 3.1.1).

4.1.5.2 Procedures for emergency unblinding

Not applicable.

4.1.6 Packaging, labelling, and re-supply

The trial drugs, enzalutamide and BI 836845, where required, will be provided by Boehringer Ingelheim, or a CRO appointed by Boehringer Ingelheim. Medication will be labelled according to the legal requirements. Medication to be administered for premedication will not be provided and must be provided by the investigational site.

For details of packaging and the description of the label, refer to the ISF.

Page 53 of 241

Proprietary confidential information. © 2022 Boehringer Ingelheim International GmbH or one or more of its affiliated companies. All rights reserved.

Drug supply and resupply for phase Ib will be managed internally by BI and/or IRT. Drug supply and resupply in the phase II randomised study will be managed via the IRT system.

4.1.7 Storage conditions

The trial drug BI 836845, and enzalutamide, must be stored in their original packaging under the storage conditions stated on the label in the hospital pharmacy in a limited access area.

4.1.8 Drug accountability

Drug supplies provided by the sponsor and/or a CRO appointed by the sponsor, must be kept in a secure, limited access storage area under the storage conditions defined by the sponsor. Where necessary, a temperature log must be maintained to make certain that the drug supplies are stored at the correct temperature.

The investigator and/or pharmacist and/or investigational drug storage manager will receive the investigational drugs delivered by the sponsor when the following requirements are fulfilled:

- approval of the study protocol by the IRB / ethics committee,
- availability of a signed and dated clinical trial contract between the sponsor and the Head of Trial Centre,
- approval/notification of the regulatory authority, e.g. competent authority,
- availability of the curriculum vitae of the principal investigator,
- availability of a signed and dated clinical trial protocol or immediately imminent signing of the clinical trial protocol, in exceptional cases, medication could already be sent to the site, before its activation via IVRS
- if applicable availability of the proof of a medical licence for the principal investigator,
- for USA availability of the Form 1572.

The investigator and/or pharmacist and/or investigational drug storage manager must maintain records of the product's delivery to the trial site, the inventory at the site, the use by each patient, and the return to the sponsor or alternative disposition of unused product(s).

These records will include dates, quantities, batch/serial numbers, expiry ('use by') dates, and the unique code numbers assigned to the investigational product(s) and trial patients. The investigator / pharmacist / investigational drug storage manager will maintain records that document adequately that the patients were provided the doses specified by the CTP and reconcile all investigational product(s) received from the sponsor. At the time of return to the sponsor and/or appointed CRO, the investigator / pharmacist / investigational drug storage manager must verify that all unused or partially used drug supplies have been returned by the clinical trial patient and that no remaining supplies are in the investigator's possession.

Proprietary confidential information. © 2022 Boehringer Ingelheim International GmbH or one or more of its affiliated companies. All rights reserved.

4.2 CONCOMITANT THERAPY, RESTRICTIONS, AND RESCUE TREATMENT

4.2.1 Rescue medication, emergency procedures, and additional treatment(s)

All concomitant (non-oncological) therapies initiated during the trial to provide adequate care to the patient, where clinically required, are allowed but should be recorded in the eCRF. Patients should receive full supportive care, e.g. transfusions of blood and blood products, antibiotics, analgesia, according to local practice/guidelines where appropriate. Trade name and indication of concomitant therapies will be documented. If patients receive parenteral nutrition during the trial, the components need not be specified in detail. It should be indicated as "parenteral nutrition" and the eCRF completed accordingly. If a patient requires anaesthesia, it will be sufficient to indicate "anaesthesia" without specifying the details.

Rescue medication to reverse the effects of BI 836845 is not available. Potential side effects of BI 836845, as well as enzalutamide, should be treated symptomatically. Please refer to the current SPC for enzalutamide for details of side-effects and management.

Symptomatic treatment of tumour-associated symptoms is allowed (including the use of bisphosphonates for treatment of bone metastases).

Anti-emetic medication should be prescribed according to local practice and according to the label instructions from the manufacturer. All anti-emetic drugs administered shall be reported in the eCRF indicating whether the respective drug is given as prophylaxis and/or premedication or treatment of an adverse event.

Premedication to avoid allergic reactions shall be administered as recommended by the manufacturer and as requested by the local requirements at the site. Administration of the drugs shall be reported in the eCRF indicating whether the respective drug is given as prophylaxis and/or premedication or treatment of an adverse event.

Precaution should be taken to avoid extravasation. Patients should be asked to report any pain or burning at the site of injection immediately. If extravasation is suspected the infusions should be stopped immediately. Treatment should be initiated according to local practice and according to the manufacturer's instructions.

Patients should be instructed about signs and symptoms of hypoglycaemia and asked to take food once they suffer from sweating, hungriness and tremor.

If elective surgery is considered necessary for the patient, at least 7 days should elapse after the last dose of BI 836845 before surgery is performed wherever possible. Treatment can be resumed on the 3rd post-operative day.

Patients that are chemically castrated before entry to the trial must continue taking luteinizing hormone release hormone (LHRH) agonists throughout the duration of the trial treatment.

For patients entering the phase Ib expansion cohort:

Enzalutamide taken by patients prior to entering the trial must be continued through the screening period up to the first day of the trial, in countries where the enzalutamide is supplied by Bohringer Ingelheim clinical trial supplies of enzalutamide will then be

Page 55 of 241

Proprietary confidential information. © 2022 Boehringer Ingelheim International GmbH or one or more of its affiliated companies. All rights reserved.

dispensed. The clinical supplies of enzalutamide must be taken by the patient continuously throughout the duration of the trial treatment.

4.2.1.1 Management of infusion reactions

Infusion reactions may occur during infusion with BI 836845 and include pyrexia, chills, rigors, dyspnoea, urticaria, bronchospasm, hypotension and hypertension and should be treated symptomatically as judged clinically relevant by the investigator.

A one hour observation period is recommended following each infusion for the first 3 cycles of treatment and at least a 15 minute observation period is recommended following subsequent infusions. Grade 1 to 2 infusion reactions may be managed with a slower infusion rate as per local guidelines. For symptomatic treatment of infusion reactions hydrocortisone, antihistamines such as chlorphenamine accompanied by an antipyretic/analgesic, and/or a bronchodilator may be administered according to the local recommendations. Severe reactions require immediate and permanent discontinuation of infusion. The grading of hypersensitivity reactions will be according to the National Cancer Institute (NCI) Common Terminology Criteria for Adverse Events CTCAE version 4.03, 14 June 2010 (R10-4848), see appendix 10.5.

Infusion reactions will not be reported on the standard AE page but will be reported on a separate page specifically for infusion reactions in the CRF.

Table 4.2.1.1: 1 Infusion reaction management

Infusion Reaction Grade	Management
CTCAE Grade 1 or 2	In the event of a mild to moderate CTCAE grade 1 or 2 non- allergic infusion event, the infusion should be interrupted immediately with symptomatic treatment (e.g., antihistamines, NSAIDs, steroids, narcotics, IV fluids) if needed. Once the
	event has resolved, the infusion should be restarted at half of the previous rate. If the reduced infusion rate is tolerated for 30 minutes, the infusion rate may then be increased to the next close rate on the patient's infusion schedule.
CTCAE Grade 3	For patients experiencing CTCAE grade 3 infusion related event, infusion should be interrupted immediately and patients should receive aggressive symptomatic treatment. Only after all the symptoms have disappeared the infusion should be started. The infusion rate at restart should be half of the infusion rate at the time of onset of the reaction.
CTCAE Grade 4	Patients experiencing CTCAE grade 4 such as anaphylaxis during an infusion should have infusion immediately stopped and receive appropriate treatment including use of resuscitation medications and equipment that must be available. Such patients should NOT receive any further BI 836845 treatment.

BI Trial No.: 1280.8 Doc. No.: c02304008-15 Trial Protocol Version 12

Proprietary confidential information. © 2022 Boehringer Ingelheim International GmbH or one or more of its affiliated companies. All rights reserved.

Page 56 of 241

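### Section 4.2.1.1 contradicts itself on severe infusion reactions, and the protocol does not say how its infusion-reaction table relates to the dose-reduction table

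*Protocol*

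**What the plan says.** Infusion reactions to BI 836845 are addressed in several places in the protocol.

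- **Section 4.2.1.1, text:** "Severe reactions require immediate and permanent discontinuation of infusion".
- **Section 4.1.4.2,** which then refers the reader to 4.2.1.1: "Severe reactions may require immediate and permanent discontinuation of infusion".
- **Table 4.2.1.1:1, grades 1–2:** for events it calls mild to moderate and non-allergic, interrupt, restart at half rate after resolution, and allow the rate to rise again if tolerated.
- **Table 4.2.1.1:1, grade 3:** interrupt and treat, then "Only after all the symptoms have disappeared the infusion should be started". The row goes on: "The infusion rate at restart should be half of the infusion rate at the time of onset of the reaction". It mentions no dose change.
- **Table 4.2.1.1:1, grade 4:** stop; "Such patients should NOT receive any further BI 836845 treatment".
- **Table 4.1.4.4:1 (dose interruption and reduction):** the triggers include "CTCAE Grade 3 or 4 toxicity" and "CTCAE Grade 2 infusion reaction despite adequate pre-medication". The action is to pause, with BI 836845 allowed to resume at a reduced dose after recovery to grade 1 or lower, or to the baseline grade.
- **Section 5.2.3:** in phase Ib escalation, a grade 2 or higher infusion reaction despite adequate pre-medication is a DLT.
- **Section 4.1.4.1:** "If a patient develops a DLT, treatment must be paused and a dose reduction must occur", with the details left to section 4.1.4.4.

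SAP Table 6.2:1, code C2, lists failure to follow the dose reduction scheme of protocol section 4.1.4.4 as a potentially important protocol violation.

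**The concern.** These are safety instructions for a weekly antibody infusion. If the text and the table beside it disagree on whether the infusion may be restarted after a severe reaction, a site has no single rule to apply, and two sites could handle the same event differently while each cites the protocol.

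The unresolved relation between the two tables raises a further question: after a reaction, is the next BI 836845 dose full, reduced or withheld? That bears on exposure in every part of the trial that gives BI 836845. In phase Ib escalation it also bears on how a patient with a DLT is treated afterwards. A site that applied only the infusion-reaction table could also be listed under SAP code C2 for not applying the other table.

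The text is still operative. The version 12 flow charts list BI 836845 infusions, and section 3.3.4.2 allows treatment up to May 2023, although section 2.3 records a sponsor recommendation of October 2021 to stop.

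**Working it through.** No formula applies, so the check sets the current passages side by side.

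**Step 1. What severe means.** No section defines it by CTCAE grade. Table 4.2.1.1:1 assigns mild to moderate to grades 1 and 2, so the next level up is grade 3. This is an inference from the protocol's own labels.

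**Step 2. Grade 3 within section 4.2.1.1.** The text requires the infusion to be stopped permanently; the table restarts it at half rate. Reading *permanent* as applying only to that day's infusion does not help, because that is the infusion the table restarts. Section 4.1.4.2 makes the same statement permissive, so the stop is mandatory in one section and optional in another.

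**Step 3. Whether Table 4.1.4.4:1 covers infusion reactions.** It names the grade 2 reaction despite pre-medication, so they are within its scope. Its grade 3/4 row carries no exception for them. The corresponding grade 3/4 item of the DLT list in section 5.2.3 does carry one. No section says which table takes precedence.

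**Step 4. The two tables, grade by grade.**

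- *Grade 1:* no infusion-reaction trigger in Table 4.1.4.4:1, so no overlap.
- *Grade 2:* the tables meet only where the event is both non-allergic (the condition in Table 4.2.1.1:1) and despite adequate pre-medication (the condition in Table 4.1.4.4:1). There, one restarts the same infusion and the other requires a pause and a reduced dose. In escalation this event is also a DLT, so section 4.1.4.1 makes the pause and reduction mandatory.
- *Grade 3:* a half-rate restart with no dose change mentioned, against a pause and a reduced dose.
- *Grade 4:* no further BI 836845, against a general row under which it may resume at a reduced dose.

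**Step 5. Range of outcomes for one grade 3 event.** Depending on the passage applied:

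- the same infusion continues at a slower rate;
- treatment pauses for up to 28 days (with an exception for clear clinical benefit, by agreement between the investigator and the sponsor's monitor), then resumes one level down in Table 4.1.4.4:2 with no return to the previous dose. That is 1000 to 750 mg, a cut of 250/1000 = 25%, or 750 to 500 mg, a cut of 250/750 = 33%;
- the infusion is stopped permanently.

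**Step 6. What code C2 does.** In SAP Table 6.2:1 the exclusion entry for C2 is none. C2 violations are identified by individual review, and SAP section 6.2 plans no per-protocol analysis. A flag therefore removes no patient from any analysis.

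**The case against.** The strongest reply has five parts.

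- **Severe might mean grade 4 only.** Table 4.2.1.1:1 reserves the ban on further drug for that grade, and section 4.2.1.1 would then be consistent. Because the term is undefined, this cannot be excluded. It is strained, though: it leaves grade 3 neither mild to moderate nor severe, and it does not explain why section 4.1.4.2 makes the stop optional.
- **The tables may be complementary.** One could govern the rate of the current infusion and the other the dose of later ones. In part this stands: a half-rate restart today and a lower dose next week can coexist. A reader might infer three mutually exclusive instructions for grade 3, and the documents do not support that. But the protocol nowhere states the split, and it would leave the conflict between text and table in section 4.2.1.1 untouched.
- **Grade 4 is hardly in conflict.** A permissive general row meets a specific prohibition, and section 3.3.4.1, item 6, requires stopping when a permanent-discontinuation criterion is met. This largely stands, so grade 4 is secondary. A reader might count grades 2, 3 and 4 as equally contradictory; that overstates grade 4, and also grade 2, which is limited to the overlap in Step 4.
- **Local discretion applies.** Appendix 10.5 refers to the protocol, local hospital guidelines, or both, and section 4.1.4.6 sends infusion procedure to the investigator site file, which is not available here. Discretion softens the practical effect but does not say which protocol sentence governs.
- **Section 4.1.4.1 adds nothing independent,** since it defers to section 4.1.4.4. That is fair; its role is to make the pause and reduction mandatory after a DLT.

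**Conclusion.** The contradiction inside section 4.2.1.1 holds: mandatory permanent discontinuation in the text against a half-rate restart in the grade 3 row. It rests on one assumption, that severe starts at grade 3, which the table's own labels imply. The missing relation between Tables 4.2.1.1:1 and 4.1.4.4:1 also holds. It is a real conflict for non-allergic grade 2 reactions despite pre-medication, an overlap at grade 3, and a secondary point at grade 4.

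The size in terms of exposure is unknown. Section 1.2.1 reports no infusion-related reactions among 81 subjects at the July 2013 cut-off. Section 2.3 says that such reactions have since been reported, but gives neither grade nor frequency. A reader might infer a material shift in Arm A dosing, or that C2 flags could distort the efficacy comparison. The documents support neither: no rate is available, and C2 excludes nobody. The point must be fixed because a safety instruction is contradictory, not because of a demonstrated effect on the results.

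**What to change.** Amend the protocol so that section 4.1.4.2, the text of 4.2.1.1, Table 4.2.1.1:1, Table 4.1.4.4:1 and the DLT pause in section 4.1.4.1 agree:

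1. Define severe by CTCAE grade.
2. Give each grade one instruction for the infusion in progress and one for later BI 836845 doses.
3. State which table governs infusion reactions, and whether the general grade 3/4 row of Table 4.1.4.4:1 applies to them.
4. Point SAP Table 6.2:1, code C2, to the governing source.

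Which clinical rule stands is for the sponsor's physicians to decide; this review proposes none. The cost is a wording amendment to the protocol and one line in the SAP, with no new procedures, data or patients.
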